7.2 Recruitment and Screening

Recruitment

The study is being advertised internally at the University of Applied Sciences and Arts Southern Switzerland SUPSI. The exact texts have been prepared according to the checklist of the Cantonal Ethics Commission Zurich.

As advertisements (text visible):

- Facebook page of the SUPSI Physiotherapy Training
<https://www.facebook.com/supsi.physiotherapie/notifications/>

Screening

Interested parties should contact the director of studies at the research office of the University of Applied Sciences and Arts Southern Switzerland (SUPSI) for an initial consultation. Interested parties will be informed about the conditions of participation, the content and procedure of the study, as well as the amount of compensation. If you are still interested, the written study information and the confirmation of consent will be handed out. Interested parties can read the written documents at their leisure and ask any questions. If you agree to the terms of the study and wish to participate in the study, bring the signed documents to the principal investigator. A copy of the signed declaration of consent (by the interested party and the study director) will be handed over to the interested party. The health questionnaire is then filled out, which clarifies the suitability of the interested party to participate in the study. If the inclusion criteria are met, the interested party has passed the screening and is admitted to participate in the study.

7.3 Group assignment

SUPSI

There will be no group assignment.

7.4 Discontinuation of study participation

If a participant withdraws from the study before the measurements have begun, the allocation lot is returned to the pot in a new envelope and a new participant is sought.

If a participant is eliminated during the measurements, all data collected up to that point will be evaluated as far as possible and included in the data analysis (in accordance with Art. 9 ClinO). In this case, no new participant will be recruited to collect the missing records.

The data will be stored encrypted with a code during the study period and evaluation of the data.

The conditions for the termination of the experiment were described in chap. 5.4.

Participants are not disadvantaged by discontinuing their participation in the study.

SUPSI

8 STUDY INTERVENTION

8.1 Medical Device ID

8.1.1 Intervention product

The Patello is a device for "Continuous Passive Motion" (CPM) of the patella. It grips the kneecap and mobilizes it in the caudal / cranial direction. Among other things, the system supports rehabilitation in the event of limited mobility of the knee joint, such as knee surgery (see Chapter 3).

The most important components of the Patello are highlighted in the following image:

[figure not shown]

Fig . 7: Patello

1. Knee brace
2. Switch panel
 - a. Slot for power plug
 - b. On/Off Switch
 - c. Reset button
3. Knee brace
4. Handheld control unit with emergency stop switch
5. Essay
 - a. Patellar Gripper
 - b. Display
 - c. Air cushion

SUPSI

6. Lifting columns

Handling Patello

1. To turn on the Patello:

Press the red on/off switch on the switch panel. The device will start initializing. After initialization is complete, the device switches to teaching mode (visible on the display).

2. Moving the grippers:

Press the "Grip" button on the hand control unit. The grippers move together until they grasp the patella from caudal and cranial.

Fig. 8: Handheld control unit

3. Operate and release the emergency stop: Switch the emergency stop toggle switch on the handheld control unit to "O". The grippers relax and the display shows the emergency stop mode. Switch the emergency stop toggle switch back to "I". Press the reset button on the switch panel.

Fig. 9: Emergency stop toggle switch

Securing the test subjects

Through the screening process (filling out the health questionnaire with examination of the inclusion and exclusion criteria), only subjects who are suitable for participation in the study are recruited. In this way, at-risk test subjects are identified at an early stage and are not recruited/included in the study.

8.1.2 Control intervention

No control intervention is carried out.

8.1.3 Packaging, labeling and use

n/a

8.1.4 Storage

SUPSI

When the patello is not in use, it is stored in a lockable cabinet.

8.2 Administration of the experiment

Since no drugs or invasive methods are used, the experiment is not discussed further in chapter 8.2-8.4 and only chapter 9 is referred to.

8.2.1 Experimental intervention

The experimental intervention (repetitive passive mobilization of the patella in the caudal / cranial direction by the patello) will be carried out on the right or left leg according to randomization.

8.2.2 Control intervention

There is no control intervention.

8.3 Dosage, application modification

In a first phase, the device settings (contact and mobilization pressure of the patello) are adjusted based on the well-being of the test subject. The mobilization pressure is built up individually to the tolerance limit so that a displacement of the patella takes place. The selected intensities are noted and maintained during all measurements per subject.

8.4 Adherence to the study intervention

The test subjects are not unnecessarily distracted by the examiners or the study director with conversations. Communication is kept to a minimum, only study-related discussions are held in order not to influence the results and to ensure homogeneity.

8.5 Follow-up treatment of eliminated participants

Data already collected from eliminated participants will be evaluated as far as possible and will be included in the data analysis of the study.

There is no disadvantage for the participants if they discontinue their participation in the study and no further interventions are necessary for follow-up treatment.

If study participation was discontinued due to an excessive reaction/injury occurring during study participation, this will be recorded and reported to the sponsor investigator (head of the research laboratory), who is also the study leader, and the supervisor of the study. If medical care is necessary, the report is forwarded to the business liability insurance of Thim van der Laan AG (Basler Versicherung) in order to ensure the appropriate follow-up treatment.

8.6 Preventive measurements

The questionnaire determines the eligibility to participate in the study by recording the inclusion and exclusion criteria.

8.7 Accompaniments

No further side effects are expected from study participation.

SUPSI

8.8 Liability

The measurements take place exclusively in the research laboratory of the University of Applied Sciences and Arts Southern Switzerland SUPSI in Landquart. Thus, there is no transport of the apparatus used or the test subjects. Liability for transport is therefore not necessary.

8.9 Return of the medical device

The Patello device is returned to the manufacturer at the end of the measurement period.

SUPSI

9 STUDY STRUCTURE & EVALUATION

9.1 Schedule Study Protocol

Table 4: Overview of the measurement process

Time	Preparation	Pre	1 Mob.	10 Mob.	20 Mob.	30 Mob.	50 Mob.
Time (min)		5	10	20	30	40	50
Measurement		1.	2.	3.	4.	5.	6.
Subject information	X						
Consent	X						
Demographics	X						
Intervention			X	X	X	X	X
Ultrasound image		X	X	X	X	X	X
Subj. Well-being		X	X	X	X	X	X

9.1.1 Measurement of primary and secondary outcomes

The primary outcome, the displacement of the patella, detected by an imaging ultrasound device (esaote MyLabClassicC, Genoa, Italy, www.esaote.com) and evaluated by a dedicated software (OsiriX, www.osirix-viewer.com), is represented in mm and is considered an objective parameter.

The secondary outcome, the recording of the subjective well-being of the test person, is determined using a visual analogue scale (VAS scale 0 - 10) and reflected in the number of cm. The value "0" describes "maximum feeling of well-being", the value "10" a "maximum feeling of discomfort". The value is considered a subjective parameter.

9.1.2 Measurement of primary outcomes

The ultrasound probe is used to record one reference point on the patella and one on the thigh (lateral epicondyle femoris) and store it as an image. After caudal mobilization, the same reference points are recorded and again stored as an image. This process is performed before the first and after each mobilization interval (1st-6th measurement). With the OsiriX software, the DICOM images obtained can be analyzed and evaluated. The distance of the displacement of the patella is shown in mm and transferred to the data sheet.

9.1.3 Measurement of secondary outcomes

Using a visual analogue scale, which goes from 0 – 10, subjective well-being is asked directly after the mobilisation intervals. The value "0" stands for "maximum well-being" and the value "10" for "maximum discomfort". The values are transferred to the data sheet.

SUPSI

9.1.4 Collection of further results

No further results will be collected.

9.1.5 Collection of safety parameters

No safety parameters are collected except for the health questionnaire.

9.1.5.1 Unfavorable Events

-

9.1.5.2 Laboratory Parameters

-

9.1.5.3 Vital signs

-

9.1.6 Collection of data in case of early termination of studies

For the participants, there is no disadvantage in the event of an (arbitrary) discontinuation of study participation and no further interventions are necessary for follow-up treatment. The data collected to date will be evaluated as far as possible and included in the data analysis (in accordance with Art. 9 ClinO).

If study participation was discontinued due to an excessive reaction/injury occurring during study participation, this will be recorded and reported to the sponsor investigator (head of the research laboratory), who is also the study leader, and the supervisor of the study. In the event of necessary medical treatment, the report is sent to the business liability insurance of Thim van der Laan AG (Basler Versicherung).

The following are recorded:

- Date and time of the incident
- Course of the incident
- Persons involved & witnesses
- Study ID (specified by the CEC)
- Personal data of the person concerned (if not previously recorded)

9.2 Procedure at each visit of the test subjects

9.2.1 Subject recruitment – screening and randomization

The study is being advertised internally at the University of Applied Sciences and Arts Southern Switzerland SUPSI. Interested parties should contact the director of studies at the research office of the University of Applied Sciences and Arts Southern Switzerland (SUPSI) for an initial consultation. Interested parties will be informed about the conditions of participation, the content and procedure of the study, as well as the amount of compensation. If you are still interested, the written study information and the confirmation of consent will be handed out. Interested parties can read the written documents at their leisure and ask any questions. If you agree to the terms of the study and wish to participate in the study, bring the signed documents to the principal investigator. A copy of the consent form signed by both parties will be given to the interested party. The health questionnaire is then filled out, which clarifies the suitability of the interested party to participate in the study. If the inclusion criteria are met, the interested party has passed the screening and is admitted to participate in the study. This is followed by the randomization of the application page by drawing lots and making an appointment for the 2 measurement days, in the same week with at least 2 days break between the measurements.

SUPSI

9.2.2 Preparation of test subjects

The test subject wears shorts and is barefoot. He sits down on the treatment table. The backrest is raised so that an upright sitting position can be assumed. The leg of the application side is placed on the patello and fixed according to the product description (Chapter 8). The foot is placed underneath so that the leg can lie relaxed. In a first phase, the contact pressure of the device is adjusted based on the well-being of the test subject. The setting is noted.

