3.1.3.2. Manual therapy Treatment Connective tissue Structures of

anterior knee joint

Manual techniques, such as those used in physiotherapy, improve the displacement of ligamentous components (Figs. 1 – 3). A finely balanced ligamentary system controls the sliding and displacement movements of the patella in the trochlea (Kyung, 2008). Both longitudinal tensile forces of the quadriceps and patellar tendon, as well as tensile forces of the lateral retinacula, which act in the transverse direction, have a load-balancing function. By directing the patella in the femoral groove, they compensate for the incongruities of the cartilage surfaces and distribute the forces over a large cross-section.

It should be added that after a knee TEP, the medial or lateral Kneecap mobilization has no effect on knee function (Ota, 2010).

In the case of structural movement restrictions, only slightly - especially in the case of pathological adhesion of the capsular fold - should be entered into the tissue resistance (*Hüter-Becker, 2009*), without provoking pain, so as not to trigger a sympathetic reflex dystrophy (*Faust, 2015*). The movement sector is continuously adjusted to the current pain threshold in order to achieve a maximum range (amplitude).

SUPSI

Fig. 1: Joint technique for femoropatellar stress pain with increasing knee flexion due to reduced sliding of the patella and translational movement in the tibiofemoral joint.

Fig. 2: The knee is bent while the examiner exerts light pressure on the patella with one hand.

Fig. 3: The knee is extended and the examiner moves the patella alternately from proximal to distal or lateral and medial under light pressure (low retropatellar compression) with limited sliding function (Winkel, 1985).

Aim of the study

The aim of this study is to determine the effectiveness of the Patello device. We would like to provide evidence of a displacement of the patella in the caudal / cranial direction by the Patello device.

The primary outcome is the objectification of the displacement of the patella measured with an imaging ultrasound device (esaote MyLabClassicC, Genoa, Italy, www.esaote.com).

As a secondary outcome, the subjective well-being of the subject is recorded, measured using a visual analogue scale (VAS scale 0 - 10).

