4.3 Secondary Objectives

Multiple measurements will be performed to detect a possible sustained and/or cumulative effect of patellar mobilization. The measurements are repeated 2x per week in the same week, with a break of at least 2 days, as described in chapter 4.2.

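### Limb position and measuring examiner are not carried from day 1 to day 2, so avoidable noise of unknown size enters the between-day comparison

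*Combined protocol and SAP*

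**What the plan says.** **Positioning (9.2.2; the Synopsis has near-identical text).** Three things are specified directly: trunk posture ("The backrest is raised so that an upright sitting position can be assumed"), foot and leg ("The foot is placed underneath so that the leg can lie relaxed"), and contact pressure ("In a first phase, the contact pressure of the device is adjusted based on the well-being of the test subject. The setting is noted"). Fixation of the leg is passed to another chapter: "The leg of the application side is placed on the patello and fixed according to the product description (Chapter 8").

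**Chapter 8.** Section 8.1.1 lists components, among them a knee brace and lifting columns. It then gives three handling steps: switching on, closing the grippers ("The grippers move together until they grasp the patella from caudal and cranial") and the emergency stop. Section 8.1.3, which covers use, is marked not applicable. Section 8.2 states that "the experiment is not discussed further in chapter 8.2-8.4 and only chapter 9 is referred to".

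**What is recorded.** Contact pressure (9.2.2) and device settings (9.2.3) go on the data sheet. Knee angle, limb position and probe site are not named.

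**Examiners.** Section 6.1.2 separates the person who applies the intervention from the person who measures. It does not require the same measurer on both days. The Synopsis lists several examiners.

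**Why there are two days.** Section 4.3: "Multiple measurements will be performed to detect a possible sustained and/or cumulative effect of patellar mobilization". Section 9.2.4 gives the same reason.

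**Device settings.** The aim text at the end of section 3.1.3.2 and section 3.6 have the settings determined afresh on each measurement day. The Synopsis and section 8.3 have them unchanged for all of a subject's measurements.

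**The concern.** The outcome is read from ultrasound images of a point on the patella and the lateral femoral epicondyle. On day 2 the leg is put on the device again, the probe is placed again, and possibly a different examiner measures. Nothing visible in the plan makes the second set-up match the first, and nothing recorded would show afterwards how far it differed.

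If set-up affects the reading, the day 2 minus day 1 difference contains set-up error as well as any lasting effect of mobilization. The main risk is loss of precision: a between-day comparison that shows nothing might be read as evidence of no sustained effect when it was merely uninformative. If set-up also shifted systematically between days, for example through a change of examiner, the difference could be biased in either direction. A position that was not recorded cannot be recovered at analysis.

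**Working it through.** **Step 1. Follow the cross-reference.** Section 9.2.2 points to Chapter 8 for fixation. Section 8.1.1 has none in its text, 8.1.3 is not applicable, and 8.2 defers sections 8.2 to 8.4 to Chapter 9. The reader returns to 9.2.2 with posture, foot support and a relaxed leg, but no angle and no fixation.

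**Step 2. Reproduce the plan's own figure.** Inputs (Synopsis): n = 30, effect size 0.68, power 0.95; significance level 0.05 (10.3.2), sidedness not stated. For a two-sided paired t-test with noncentrality d√n = 0.68 × √30 = 3.72 on 29 degrees of freedom, power is 0.949. The stated figure therefore reproduces as a paired comparison with d in units of the SD of the differences. A one-sided test would give 0.977.

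**Step 3. What cancels.** Let o be the day's set-up offset and e the reading error of each image.

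- Same-day displacement = (o + shift + e₂) − (o + e₁). The offset drops out.
- Raw starting distance, day 2 minus day 1 = (o₂ + e) − (o₁ + e′). The offset stays.

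Illustration with an assumed reading error of SD 0.5 mm per image and an assumed per-day offset of SD 3 mm:

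| Quantity (day 2 minus day 1) | SD without offset | SD with offset |
|---|---|---|
| Raw starting distance | √(2 × 0.25) = 0.71 mm | √(2 × 0.25 + 2 × 9) = 4.30 mm |
| Displacement | √(4 × 0.25) = 1.00 mm | 1.00 mm |

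A simulation gave 4.31 and 1.00 mm with the offset. So two between-day questions behave differently:

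- *Sustained shift of the patella at the start of day 2.* Displacement against the same day's first image is zero at measurement 1 by construction. This question can be answered only from raw distances, where the offset counts in full.
- *Larger reachable displacement on day 2.* The offset cancels. Only the part of set-up error that changes displacement itself remains (dependence on knee angle, probe placement or examiner).

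**Step 4. Size, free of any millimetre scale.** Let s be the SD of the day difference without set-up noise and p the per-day noise SD that does enter the quantity compared. The SD becomes √(s² + 2p²). Take a true day difference of 0.68 s, n = 30, two-sided 0.05:

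| p / s | SD of day difference | Effective d | Power |
|---|---|---|---|
| 0 | 1.00 s | 0.680 | 0.95 |
| 0.5 | √1.5 = 1.22 s | 0.555 | 0.84 |
| 1 | √3 = 1.73 s | 0.393 | 0.55 |
| 2 | √9 = 3.00 s | 0.227 | 0.22 |

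The documents do not say which row applies.

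**The case against.** **The primary comparison is not touched.** The hypotheses in 10.1 contrast repeated with single mobilization, and Factor 2 in 10.3.2 is the six measurements of one session. There is no day factor, and 10.3.3 plans no secondary analysis. This stands: the noise affects a stated aim, not a specified test. The absence of any between-day analysis is a separate and more basic gap, but adding that analysis later would not supply positions that were never recorded.

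**The missing text may exist elsewhere.** Fig. 7 is not shown in the copy reviewed, some pages before section 1.7 are unavailable, and the data form is an enclosure. A pictured leg position or an examiner assignment cannot be excluded. This stands as a limit. A picture alone, however, would not establish that each subject's position is recorded and reproduced.

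**The evidence on knee angle is thin.** The words "with increasing knee flexion due to reduced sliding of the patella" come from a figure caption about a manual technique for a painful joint. They bring flexion and sliding together but do not say that resting patellar position follows knee angle. No section says that the lifting columns or brace set that angle. This also stands, and it is why the dependence is put here as a possibility.

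**A stronger reading a reader might infer** is that millimetres of positioning error enter the between-day result and power falls to 42–75%. That range needs four assumed inputs: a patellar arc of 20–30 mm radius, an SD of 5 degrees for the day-to-day angle difference, a base SD of 1.0–1.5 mm and a true change of 1 mm. None is in the documents. With an SD of 3 degrees the same formula gives 68–96%, and with 2 degrees 83–99%. It also puts the whole starting-position shift into the SD, which step 3 shows is right only for raw distances compared across days, a comparison the plan does not specify.

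**Conclusion.** The point holds as a gap in procedure that weakens a stated secondary objective. In the readable text, limb position is only partly specified, is not recorded or reproduced, and the measurer is not held constant across days. The within-session comparison is largely protected.

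The size is unknown. The power loss from 0.95 to 0.84 or 0.55 is conditional on per-day noise of half or all of the base SD, independence between days, and a two-sided paired comparison that is not itself in the plan. The documents do not support a statement that the noise is of millimetre size.

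The conflicting statements on device settings bear on the same objective: if settings differ between days, matched positioning alone does not make the days comparable. Those sections must be reconciled. The change is worth making because it is cheap and the information cannot be obtained afterwards.

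**What to change.** In 9.2.2:

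1. After positioning on day 1, record knee angle (goniometer), device and foot position, and probe site on the data sheet.
2. On day 2, reproduce these before the first image, with the angle within a tolerance stated in advance.
3. Use one measuring examiner per subject for both days. This fits with the separation of operator and measurer in 6.1.2.
4. Report the day 2 angle deviation beside any between-day result.
5. Replace the reference to Chapter 8 with the fixation instruction itself, or add that instruction to 8.1.1.

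Also reconcile the aim text in Chapter 3 and section 3.6 with the Synopsis and section 8.3 on whether device settings are determined anew each day or kept throughout.

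Cost: about one minute per visit, a few data-sheet fields and a scheduling constraint on examiners.

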9.2.3 Sequence of the measurements

After determining the contact pressure, the pre-mobilization measurement is carried out (**1st measurement**). The ultrasound probe is used to visualize a reference point on the patella and at the same time the lateral femoral epicondyle on the thigh and save it as an image. Afterwards, the mobilization pressure is built up individually up to the tolerance limit of the test subject so that a displacement of the patella caudally takes place. The maximum deflection of the patella to the reference point on the thigh is determined, the device settings are noted and transferred to the data sheet (**2nd measurement**).

As described above, further measurements are carried out according to the following scheme: after 10 mobilisations (**3rd measurement**), after 20 mobilisations (**4th measurement**), after 30 mobilisations (**5th measurement**) and after 50 mobilisations (**6th measurement**).

Table 5: Overview of the course of studies

Time	Preparation	Pre	1 Mob.	10 Mob.	20 Mob.	30 Mob.	50 Mob.
Time (min)		5	10	20	30	40	50
Measurement		1.	2.	3.	4.	5.	6.
Subject information	X						
Consent	X						
Demographics	X						
Intervention			X	X	X	X	X
Ultrasound image		X	X	X	X	X	X
Subj. Well-being		X	X	X	X	X	X

